#### **For all records excluding the last chronological record for a condition/event**

- AE condition end date will be imputed as the start date of the subsequent record

#### **For the last chronological record for a condition/event**

- If outcome is “recovered/resolved”, “recovered/resolved with sequelae”, or “fatal” apply the following:
  - If only year is provided for the end date and year is equal to the year of the last dose date:
    - AE condition end date will be imputed as the minimum of (last dose date+30, death date, data extraction date, December 31st of the end date year)
  - If only year is provided for the end date and year is not equal to the year of the last dose date:
    - AE condition end date will be imputed as the minimum of (death date, data extraction date, December 31st of the end date year)
  - If month and year are provided for the end date:
    - AE condition end date will be imputed as the minimum of (death date, data extraction date, last day of the end date month/year)
- If outcome is “recovering/resolving”, “not recovered/resolved”, “unknown”, or blank:
  - AE condition end date will not be imputed.

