3. No other immediately apparent possible causes of aminotransferase elevation and hyperbilirubinemia, including, but not limited to, viral hepatitis, pre-existing chronic or acute liver disease, or the administration of other drug(s) known to be hepatotoxic.

Reporting Requirements

Any potential Hy's Law case should be handled as a suspected unexpected serious adverse reaction (SUSAR) associated with the use of the drug and reported promptly to the sponsor.

Reporting should include all available information and should initiate close follow-up until complete resolution of the problem and completion of all attempts to obtain supplementary data.

Follow-up for Abnormal Laboratory Results Suggesting Potential DILI

In general, an increase of serum ALT or AST to $>3 \times$ ULN should be followed by repeat testing within 48 to 72 hours of serum ALT, AST, alkaline phosphatase, and total bilirubin, to confirm the abnormalities and to determine whether they are worsening.

Appropriate medical assessment should be initiated to investigate potential confounding factors and alternative causes of hepatotoxicity.

7.7.8.3 Reporting Periods for Adverse Events, Serious Adverse Events, and Adverse Events of Special Interest

The safety reporting period for all AEs and SAEs is from study Day 1 (predose) through the EOT visit or 30 days after the last study treatment (tisotumab vedotin), whichever is later.

However, all study protocol-related AEs are to be recorded from the time of informed consent. All SAEs that occur after the safety reporting period and are considered study treatment-related in the opinion of the investigator should also be reported to the sponsor.

SAEs will be followed until significant changes return to baseline, the event stabilizes (recovering/resolving) or is no longer considered clinically significant by the investigator, or the patient dies or withdraws consent. All non-serious AEs will be followed through the safety reporting period. Certain non-serious AEs of interest (i.e., all ocular events) will be followed until resolution, return to baseline, or study closure.

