#### **7.6.1.1 Adverse Events of Special Interest**

Adverse events of ocular AEs, peripheral neuropathy, and bleeding are considered AESI. The search criteria for AESI will be maintained in a separate document and will be finalized prior to database lock. Shift tables comparing the highest post-baseline to baseline CTCAE grade will be presented when applicable.

Time to onset will be summarized for subjects who have the events that meet certain search criteria. Time to onset is defined as time (days) from the date of first dose to the start date of first event (start date of first event – date of first dose + 1).

Time to resolution will be summarized for events that meet certain search criteria and have the outcome of ‘recovered/resolved’ or ‘recovered/resolved with sequelae’. Time to resolution is defined as time (days) from the start date of the event to the end date of the same event (end date of the event – start date of the event + 1).

For events that are not resolved, improvement is defined as a decrease by at least one grade from the worst grade as of the latest assessment. For events that meet the definition of ‘improvement’, time to improvement will be calculated as time from the worst grade of the event to the date the event is improved.

Time to onset, resolution and improvement will be summarized by descriptive statistics (mean, standard deviation, median, minimum, and maximum). Time to onset will be summarized at the subject level. Time to resolution and improvement will be summarized at the event level.

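### The SAP rule for year-only AE end dates has no check against the record's own start date, so it can put an end before its start in AESI time to resolution

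*SAP*

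**What the plan says.** SAP Appendix A imputes a partial end date on the last chronological record of an event only if the outcome is resolved, resolved with sequelae, or fatal. There are three branches:

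- Year alone known, matching the last-dose year: "AE condition end date will be imputed as the minimum of (last dose date+30, death date, data extraction date", with 31 December of the end year as the last term.
- "If only year is provided for the end date and year is not equal to the year of the last dose date": the same minimum without the last-dose term.
- Month and year known: "AE condition end date will be imputed as the minimum of (death date, data extraction date, last day of the end date month/year"), again without the last-dose term.

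No branch compares the result with the start of the record. The same appendix imputes start dates before end dates and lets an end date influence the start only if it is complete. A start with a known month but no day goes to the last day of that month, unless that is the month of first dose or a complete end date is earlier.

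Protocol 7.7.8.3 sets the follow-up: "Certain non-serious AEs of interest (i.e., all ocular events) will be followed until resolution, return to baseline, or study closure". SAEs are followed until they return to baseline, stabilise or lose clinical significance, and late treatment-related SAEs are still reported. AE collection in general runs "through the EOT visit or 30 days after the last study treatment (tisotumab vedotin), whichever is later". Protocol 6.6 places EOT at 30 to 37 days after last dose and allows it to be later.

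SAP 7.6.1.1 names ocular AEs as AESI and states: "Time to resolution is defined as time (days) from the start date of the event to the end date of the same event", plus one day, summarised for events with a resolved outcome.

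**The concern.** The ceiling of last dose + 30 days is shorter than the period over which the protocol allows AEs to start, change grade and resolve. Where a record starts after that ceiling, the rule produces an end date that cannot be true. Where an event is recorded as ongoing after it, the rule produces an end date that the trial's own data contradict. Both results go into time to resolution for the AESI, and ocular toxicity is a central safety question for the dose-dense regimen. A negative duration would also distort the mean and minimum that SAP 7.6.1.1 asks for.

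**Working it through.** **Checking the reading of the appendix.** Applying the start-date rules literally to the SAP's Example 1 returns its imputed starts: 31DEC2011, 31MAY2012, 30JUN2012 and 30JUN2012. Neither worked example uses the year-only, same-year branch, so the SAP gives no figure for that branch to reproduce.

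**Inputs.** The rules are as described above. The dates are assumptions for illustration: last dose 16 March 2020, data extraction 30 June 2021, no death, end date recorded as 2020 only, outcome resolved.

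Cap = 16 March + 30 days = 15 April 2020. This is earlier than 31 December 2020 and the extraction date, so the imputed end is 15 April 2020 in every case.

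Duration = end - start + 1.

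| Case | Record start | Calculation | Duration (days) |
|---|---|---|---|
| A. Ocular AE with onset on treatment | 10 Mar 2020 | 15 Apr - 10 Mar + 1 | 37 |
| B. Onset at last dose + 35, before a delayed EOT | 20 Apr 2020 | 15 Apr - 20 Apr + 1 | -4 |
| C. Final severity record starting at last dose + 60 | 15 May 2020 | 15 Apr - 15 May + 1 | -29 |
| D. Start known only as April 2020, set to 30 April | 30 Apr 2020 | 15 Apr - 30 Apr + 1 | -14 |

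**Case C at event level.** Example 1 shows one event split into several severity records. Suppose the records are joined, and the event in case C began on 10 March. The result is then 37 days, as in case A. But the last record starts on 15 May, so the event lasted at least 15 May - 10 March + 1 = 67 days. The duration is positive but contradicted by the data.

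**How easily case D arises, given its trigger.** Take a month-only start in the month that contains last dose + 30, where that is not the month of first dose. The end precedes the start unless last dose + 30 is itself a month end. Last-dose dates from 1 January to 1 December 2020 keep the cap within 2020: 336 dates. Twelve of them put the cap on a month end, leaving 336 - 12 = 324 that fail. The true onset in case D may lie within 30 days of last dose.

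**Whether another rule rescues these records.** The start is fixed first, and a partial end date cannot pull it back. The sorting step changes start days and does not constrain the end. SAP 6.5 has an end-before-start correction, but only for prior-therapy end dates.

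**With a floor.** Imputed end = later of the capped date, the record's start, and the last date recorded as ongoing. Cases B, C and D each become 1 day at record level, and the joined event in case C becomes 67 days. Case A stays at 37 unless a later ongoing date is on file.

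**Removing the cap instead.** The end becomes 31 December 2020, and case A becomes 31 December - 10 March + 1 = 297 days. If case A truly resolved 100 days after last dose (24 June, 107 days), the cap is 107 - 37 = 70 days too short and its removal is 297 - 107 = 190 days too long.

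**The case against.** The trigger is narrow. It needs the last record, a resolved or fatal outcome, both day and month missing, and an end year equal to the last-dose year. Ocular events are among the least likely to meet it: all go to the sponsor within 24 hours (Protocol 7.7.8.4), an ophthalmologist follows them to resolution (5.3.1), their medications are documented until resolution (5.5), and eCRF queries are raised (8.2). This stands, and it keeps the point small.

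An event starting more than 30 days after last dose is not treatment-emergent (SAP 7.6.1), so case B may never be tabulated. This stands only in part. SAP 7.6.1.1 does not expressly limit time to resolution to treatment-emergent events. Case C can concern an event that began on treatment, and case D one whose true onset was within 30 days.

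A reader might go further and infer that the rule shortens ocular events and that the last-dose term should be deleted. The documents do not support that. An event known only to have ended in a given year may have ended before last dose + 30, so truncation is possible rather than certain. Deletion defaults to 31 December unless death or extraction is earlier, and in case A that misses by more than the cap does. Contrasting the capped and uncapped year-only branches on one record is also not like for like. Moving the last dose into the previous year moves the onset to a different distance from dosing.

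**Conclusion.** The rule is wrong as written in one limited respect: it can return an end date earlier than the record's start, or earlier than a date on which the event was still recorded as ongoing. This follows from the text alone. The sizes shown (-4, -29 and -14 days, and 37 against at least 67) rest on assumed dates. The documents do not say how often year-only end dates occur, so the effect on the summary cannot be estimated; it is probably a handful of records at most.

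The consequence is confined to AE durations and the descriptive AESI time-to-resolution summary. Confirmed ORR does not use these dates, treatment-emergent status is set by onset, and no decision rule depends on time to resolution. Whether the last-dose term is a good convention for ocular events is a matter of choice between two imperfect defaults. This is a minor correction.

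**What to change.** In SAP Appendix A, add to the end-date rules for the last record: the imputed end date is not earlier than the known or imputed start date of that record, nor earlier than the last date on which the event was recorded as ongoing. The start-date part extends to AEs the kind of guard that SAP 6.5 applies to prior therapies; the ongoing-date part is new. The floor should not pass the death or extraction date. If a month-end start lies beyond either, the start is what needs correcting.

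Flag imputed durations in the AESI time-to-resolution table, since a floored duration is a minimum and not an observation. At most, add a sensitivity summary showing year-only ocular end dates with and without the last-dose term. The term need not be removed.

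The cost is one sentence in the SAP, a short programming check and a table footnote, made before database lock. No site procedure or data collection changes.

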**Example 1**

**AESPID 1: Condition/Event HEADACHE**

**First dose date 01JAN2012**

**Prior to imputation**

Start date	Condition end date	Severity	Outcome	Onset
UNUNK2011	15APR2012	1	not recovered/resolved	pre-ICF
15APR2012	UNMAY2012	2	recovering/resolving	post 1st dose
UNMAY2012	UNJUN2012	1	not recovered/resolved	post 1st dose
UNJUN2012	UNJUN2012	3	recovering/resolving	post 1st dose
UNJUN2012	10JUL2012	2	recovering/resolving	post 1st dose
10JUL2012	--	1	not recovered/resolved	post 1st dose

**Post imputation**

Start date	Condition end date	Severity	Outcome
31DEC2011	15APR2012	1	not recovered/resolved
15APR2012	31MAY2012	2	recovering/resolving
31MAY2012	30JUN2012	1	not recovered/resolved
30JUN2012	30JUN2012	3	recovering/resolving
30JUN2012	10JUL2012	2	recovering/resolving
10JUL2012	--	1	not recovered/resolved

*Example 2 (highlights choice of last day of the month as opposed to the 1st or the 15th)*

**AESPID 4: Condition/Event NAUSEA**

**First dose date 01APR2012**

**Prior to imputation**

Start date	Condition end date	Severity	Outcome	Onset
UNUNK2011	25APR2012	1	not recovered/resolved	pre-ICF
25APR2012	UNAPR2012	2	recovering/resolving	post 1st dose
UNAPR2012	04MAY2012	1	recovered/resolved	post 1st dose

**Post imputation**

Start date	Condition end date	Severity	Outcome
31DEC2011	25APR2012	1	not recovered/resolved
25APR2012	31APR2012	2	recovering/resolving
31APR2012	04MAY2012	1	recovered/resolved

## **Appendix B IMPUTATION OF PARTIALLY MISSING SUBSEQUENT ANTICANCER THERAPY START DATE**

The algorithm below should be used to impute subsequent anticancer therapy start dates for which only day is missing.

- If the month and year of the start date of subsequent anticancer therapy are the same as the month and year of a response assessment date, and
  - If the response is a PD, subsequent anticancer therapy start date will be imputed as the response assessment date or the day after the last study treatment, whichever is later.
  - If the response is not a PD, subsequent anticancer therapy start date will be imputed as the first day of the month or the day after the last study treatment, whichever is later.
- Else if the month and year of the start date of subsequent anticancer therapy are the same as the month and year of the end date of last study treatment, subsequent anticancer therapy start date will be imputed as the day after the last study treatment end date.
- Else if the start date of subsequent anticancer therapy is later than the end date of last study treatment based on available month and year, subsequent anticancer therapy start date will be imputed as the first day of the month.
